Aim 2: The enrolled patients will be followed daily by our trained clinical research coordinator. Patient's subjective pain scores will be assessed and documented by the trained nursing staff using Visual Analogue Scale (VAS) daily. Morphine milligram equivalent (MME) along with other pain medication intake will be recorded per day for the duration of Ketorolac or placebo therapy. Patient's clinical course will be monitored closely and daily to ensure no NSAIDs will be administered to the control cohort to ensure consistency and protocol adherence of the study. Once patients are discharged from the hospital, outpatient pain scores will be assessed during routine clinic follow up visits using Patient-Reported Outcomes Measurement Information System (PROMIS) surveys. Opioid and pain modulating medication prescription refills will be monitored using the State All Scheduled Prescription Electronic Reporting system. Patient narcotic requirement will be assessed during all of the routine follow up visits by the same research coordinator in order to maintain consistency. Patients' inpatient and outpatient subjective pain score and MME intake will be compared between the control and treatment groups using two-tailed independent t-tests.

Aim 3:

Finally, analysis will be performed to evaluate the treatment effects between two groups using fracture unions as a dependent variable. The rate of fracture unions will be calculated at 3 month, 6 month and 12 month. Fractures will be considered united if they met the criteria for clinical or radiological union. The baseline clinical factors that are independently associated with fracture unions will be assessed from candidate variables and are entered using a forward ($p<0.05$) and backwards ($p<0.10$) stepwise selection procedure. Finally, the multivariate model will be performed to assess the association of clinical factors with fracture unions starting at 3 month between two groups.

Attachments

Data Collection & Research Materials

In this section, please provide the following:

- Describe all sources or methods for obtaining research materials about or from living individuals (such as specimens, records, surveys, interviews, participant observation, etc.), and explain why this information is needed to conduct the study.
- For each source or method described, please list or attach all data to be collected (such as genetic information, interview scripts, survey tools, data collection forms for existing data, etc.).

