- k. Patients with chronic use of steroids or immune modulating drugs or history of organ transplantation
- l. Patients with preexisting chronic renal, liver, or lung disease
- m. Patients with history of myocardial infarctions
- n. Patients with chronic heart failure
- o. Patients with allergy to NSAID
- p. Patients with coagulation defects (e.g., clotting factor deficiencies, thrombophilia, or any bleeding disorder)
- q. Patients receiving chronic opioid therapy or treatment for opioid use disorder.

6. Sample Size Calculation

Pretrial sample size calculations were performed regarding LOS because this will be the primary outcome measure of the clinical trial. Using a significance level of 0.05 and an assumed SD of 1.5 days, a sample size of 42 patients per group (84 total) would yield 80% power to detect a difference of 0.928 days in average LOS between the placebo and ketorolac groups. Allowing for a dropout rate up to 25%, the target enrollment will be 112 patients total, with 56 patients per group. Power calculations were performed using nQuery 8.5 (Statistical Solutions Ltd; Cork, Ireland).

7. Statistical Analysis Plan

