Group-level summary statistics will be calculated for demographic and clinical variables, and differences between the 2 groups will be evaluated using two-sample t-tests for quantitative measures and Fisher exact tests for categorical measures, as appropriate. LOS and MME values will be summarized using medians and interquartile ranges for each group. Group-level VAS pain scores will be summarized using means and standard deviations. An analysis of variance model will be fit to compare log-transformed LOS between the 2 groups. Linear mixed models will be used to estimate differences in VAS pain scores and log-transformed MME values over time between the 2 groups. Time and group comparisons for each cytokine will be made using linear mixed models, with and without adjusting for selected covariates. Patient demographic variables will be considered for inclusion as covariates in each model but will only be retained if they significantly improve the model. Linear mixed models may be log-transformed, double-log-transformed, or square-root-transformed to correct for right skewness, as appropriate. Likelihood ratio testing and Akaike information criterion will be used to select appropriate covariance structures in each case. A Kenward–Roger adjustment will be used to correct for negative bias in the standard errors and degrees of freedom calculations. Throughout the study, a P value of less than 0.05 will be considered significant. All analyses will be completed in SAS 9.4 (SAS Institute Inc.; Cary, NC).

8. Study-Wide Recruitment Methods

Potential patients will be prospectively identified either at the time of the initial consultation, at the morning fracture conference, based on the orthopaedic injury diagnosis (inclusion criteria noted above). Patients will be screened by their inclusion and exclusion criteria and will be considered for enrollment in the study should they meet study criteria.

9. Study Timeline

After arrival, patient screening and enrollment is expected within 12 hours of arrival to ensure initial blood draw. Further participation of subjects will include blood draws and ketorolac administration through day 5. Patient participation will continue through to their follow-up visits and conclude with their 6 weeks post discharge clinic visit. Detailed project timeline and schedule of activities is listed in Table 1.

Tentative time table of the proposed project												
Procedures	Enrollment	Inpatient						Outpatient				

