Patients with pre-existing medical co-morbidities and contraindications to ketorolac will be excluded from the study (see 5 for detailed exclusion criteria)

Patients in the treatment group will receive 15 mg IV ketorolac every 6 hours for 5 days after admission.

e. **Post-operative inpatient care:** Enrolled patients will have daily blood samples (10 cc) will be collected post-admission and at 24 hours intervals for 5 days by blinded health care personnel. The initial blood sample will be collected within 12 hours of initial injury and before the first scheduled administration of ketorolac to establish baseline cytokine profile. Subsequent blood sample collection will be 24 hours apart. Medication compliance and monitoring will be performed daily by the same research coordinators.

Sandwich ELISA will be used to determine the concentrations of IL-1, IL-6, IL-10, and PGE2 in obtained blood samples. Blinded quality control samples will be included in every batch for each ELISA assay. This will allow for the calculation of coefficient of variation (CV) within and across patient cohorts. In the present study, the CV will be calculated for IL-1, IL-6, IL-10, and PGE2. If wide variations are observed among the analytes during the analysis, we will restrict our analysis to analytes in which the CV is less than 20%.

In addition to the standard trauma labs (Sodium, Potassium, Creatinine, Lactic acid, Glucose, Platelet, blood urea nitrogen (BUN), hematocrit, and white blood cell count), patient demographics (sex, age, and BMI), injury data (mechanism of injury, NISS, and types of surgical/procedural interventions), posttraumatic complications (occurrence of bacterial pneumonia, ARDS, SIRS, MODS), complications defined in the National Trauma Dataset, and inflammatory data will be collected. This data will be maintained in our clinical database (REDCap) by a full-time Clinical Study Coordinator.

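### Section 7's keep-if-significant rule for demographic covariates can lift the treatment test slightly above 5% and leaves the primary model unnamed; a fixed list is a cheap improvement

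*Combined protocol and SAP*

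**What the plan says.** Section 7 (Statistical Analysis Plan) plans an analysis of variance on log LOS, linear mixed models for VAS and log MME, and linear mixed models for each cytokine. It then says that patient demographic variables "will be considered for inclusion as covariates in each model but will only be retained if they significantly improve the model". The significance rule is "Throughout the study, a P value of less than 0.05 will be considered significant", with no allowance for the selection step.

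Section 7 does not list the candidates. Section 10(e) names the demographics collected as "patient demographics (sex, age, and BMI", which makes three. Section 7 also leaves open:
- the test and threshold for retaining a covariate;
- whether treatment is in the model while covariates are tested;
- whether selection is done blind to arm;
- whether the adjusted or the unadjusted result is primary.

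The cytokine comparisons are planned in both forms, with neither ranked above the other. The sentence on LOS mentions no covariate, so only the reference to each model brings the primary outcome under the rule.

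**The concern.** The covariate set is chosen from the same outcome data that are then used to test treatment, and the test takes no account of that choice. Two things are at stake.

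1. **Error rate.** If a covariate is kept or dropped after looking at a model that contains treatment, the decision is tied to the chance imbalance between arms, and so to the treatment estimate. The nominal 5% level is then not guaranteed.
2. **Discretion.** LOS, VAS, MME and each cytokine can end up adjusted for different variables. With no primary version named, adjusted and unadjusted results both stand as candidates for the headline.

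**Working it through.** **Step 1. Reproduce the plan's sample size (Section 6).** The plan takes alpha 0.05 and an SD of 1.5 days, and says that 84 evaluable patients, 42 in each arm, "would yield 80% power to detect a difference of 0.928 days in average LOS". Sections 6 and 7 do not state sidedness. The Aim 2 text in the IRB application is two-tailed, and two-sided 0.05 reproduces the stated N.
- Noncentrality = 0.928 / (1.5 × √(2/42)) = 0.928 / 0.3273 = 2.835.
- Two-sample t-test power at 42 per arm = 80.0%, as stated.
- Enrolment = 84 / (1 − 0.25) = 112, as stated.

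The standardised effect used below is 0.928 / 1.5 = 0.619 SD.

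**Step 2. Simulate the retention rule.** The model is a 1:1 linear model with N = 84, SD 1.5 and three independent baseline covariates, one of them binary. Selection is by backward elimination at P<0.05. Total R² is an assumption, varied from 0 to 0.30, because the documents give no figure. There were 100,000 trials per null setting (Monte Carlo SE √(0.05 × 0.95 / 100,000) ≈ 0.0007) and 30,000 per power setting (SE about 0.002).

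Type I error, %:

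| Total R² | All three fixed | Selected, treatment in model | Selected, treatment not in model | Smaller P of unadjusted and selected (treatment in model) |
|---|---|---|---|---|
| 0 | 5.0 | 5.1 | 5.0 | 5.2 |
| 0.05 | 5.1 | 5.6 | 5.0 | 6.1 |
| 0.10 | 5.0 | 5.7 | 4.9 | 6.6 |
| 0.20 | 5.1 | 5.7 | 4.9 | 7.5 |
| 0.30 | 5.0 | 5.2 | 5.0 | 7.7 |

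A separate run at R² 0.10-0.20 gave 5.3-5.4% with treatment in the model, 4.7-4.8% without it, and 4.7-4.9% with fixed covariates. The range for modest prognostic value is therefore about 5.3-5.7%. Coverage is its complement: 100 − 5.7 = 94.3% to 100 − 5.3 = 94.7%.

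**Step 3. Find the cause.** At R² 0.10 the mean interval width is 1.2487 with treatment in the model during selection and 1.2492 without it. The widths are practically equal, yet the errors are 5.7% and 4.9%. Narrower intervals therefore do not explain the excess. It comes from letting the treatment term influence which covariates stay. Under the null, a set chosen without reference to arm is independent of the randomised assignment, so the later treatment test keeps its level.

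**Step 4. Power at the stated effect, three candidates, %.**

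| Total R² | Fixed | Selected, treatment in model |
|---|---|---|
| 0 | 78.8 | 80.3 |
| 0.05 | 80.3 | 81.1 |
| 0.10 | 82.8 | 82.6 |
| 0.20 | 87.0 | 86.4 |
| 0.30 | 90.8 | 90.5 |

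These figures do not correct for the higher error of selection. A smaller size-matched check (15,000 null and 8,000 power trials, noise about 1 point) gave 80.6, 81.4 and 86.6% with selection at R² 0.05, 0.10 and 0.20. Fixed covariates gave 81.6, 83.1 and 88.0%. Selection led only at R² 0, by 78.7% to 77.5%. When selection ignores treatment, power is about 1.5-2 points below fixed covariates at R² 0.10-0.20.

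**Step 5. Cost of fixing three useless covariates.** Residual degrees of freedom are 84 − 2 − 3 = 79. The variance of the treatment estimate rises by about 3/79 = 3.8%, and its standard error by √1.038 = 1.019. Noncentrality falls to 2.835 / 1.019 = 2.78, and power falls from 80% to about 78.5%. Simulated values were 78.8% and 78.2%.

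**The case against.** The strongest reply is that the inflation depends on a detail the plan does not give. If covariates are chosen without treatment in the model, the 5% level holds, and nothing in Section 7 excludes that. This stands. A reader might infer that none of the Section 7 models holds its level, but the documents do not support that. They leave the procedure open, and only one reading inflates the error.

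Other points that stand:
- **Size.** With the three demographics of Section 10(e) the excess is under one percentage point. Errors around 6% appear only with five or six candidates, and Section 7 lists no such set.
- **Power.** A reader might infer that selection never gains power over fixed covariates. It does when covariates are useless or weak: by 1.5 points at R² 0 and 0.7 at R² 0.05 in nominal terms, partly bought by the higher error.
- **Intervals.** Narrowing against fixed covariates is at most about 2% with three candidates and nil by R² 0.20. Section 7 mentions no confidence intervals, so no stated coverage is breached.
- **Timing.** A reader might infer that models will be picked after unblinding. The plan gives no timing for selection, and Section 2 masks the investigator. The choice is open; misuse is not shown.
- **Reach.** LOS comes under the rule only through a general phrase, and the mixed models were not simulated.
- **Alternatives.** Selecting blind to arm, or making the unadjusted model primary, would also hold 5%.

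The reply does not remove the concern. Asking whether a variable improves a model most naturally refers to the model that contains group. The alternatives give up power when the covariates are prognostic, and the unadjusted cytokine models already planned are not labelled as primary or sensitivity.

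**Conclusion.** The point holds in a limited form. If retention is tested with treatment in the model, the treatment test runs at about 5.3-5.7% instead of 5% when three demographics have modest prognostic value. If it is tested without treatment, the level holds but about 1.5-2 points of power are given up against fixed covariates at R² 0.10-0.20. If the covariates predict nothing, the rule does little harm.

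The larger exposure is the unnamed primary version: taking the better of the adjusted and unadjusted results would raise the error to as much as about 7.7% with three candidates. That is what the freedom could cost, not something the plan says will be done.

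These figures rest on assumed R² values, independent covariates, a 0.05 retention threshold and a single-outcome linear model on the Section 6 scale. They were not derived for the mixed models, nor for the choice of transformation or covariance structure. This is a cheap improvement, not a flaw that invalidates the trial.

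**What to change.** Replace the retention sentence in Section 7 with a fixed rule, for example: *Sex, age and BMI enter every between-arm model (log LOS, VAS, log MME and each cytokine) whatever their P values. This adjusted model is the primary analysis of that outcome. The same model without the three covariates is reported as a sensitivity analysis.* Say explicitly that the LOS model is included.

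The IRB application (Research Procedures, Aim 1) gives a different covariate list for its Poisson and logistic models, so state that Section 7 governs the models it describes.

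The application shows that enrolment has closed and that VAS and opioid comparisons on 70 participants have been reported. The change should therefore be dated and disclosed as made at that stage.

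The cost is a short text change using variables already collected, and about 1.5-2 points of power if none of the three predicts the outcome.

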If your study is monitored by a DSMB or under a DSMP, attach all documentation (i.e. summary report; meeting minutes) representing Data and Safety Monitoring activities that have not been previously reported to the IRB.

Attachments

7. Since the most recent IRB Initial/Continuation Review Approval:

Have there been any **participant complaints** regarding the research?

Yes No

If yes, in the field below, provide a summary describing the complaints.

Have any **subjects withdrawn** from the research voluntarily or by you as the PI for reasons related to safety, welfare, or problems related to the conduct of the research? If a participant does not meet the screening criteria for a study even if they signed a screening consent it is NOT considered a withdrawal.

Yes No

If yes, in the field below, provide a detailed explanation to the withdrawal(s) including if participants were lost to contact.

Has any **new and relevant literature** been published since the last IRB review, especially literature relating to risks associated with the research?

Yes No

If yes, attach a copy of the literature as well as a brief summary of the literature including, if pertinent, the impact of the findings on the protection of human subjects.

Attachments

Have there been any **interim findings**?

Yes No

If yes, attach a copy of **Interim Findings**.

Attachments

Attach Type	File Name
Interim Findings	OTA IM Abstract VAS and MME 2.10.23.docx

Have **subjects experienced any benefits**?

Yes No

If yes, in the field below, provide a description of benefits subjects have experienced.

Results:

In total, 70 participants were enrolled, with 35 randomized to the ketorolac group and 35 to the placebo group. Study groups were balanced with respect to age, BMI, and NISS. Over the 5-day treatment period, average opioid intake ($p = 0.0039$) and VAS pain scores ($p = 0.0481$) were significantly reduced in the ketorolac group compared to the placebo group. The ketorolac group experienced a 43.2% reduction in mean MME compared to the placebo group.

Conclusion:

Scheduled, short-term use of low-dose ketorolac was associated with significantly reduced opioid use and pain in orthopedic polytrauma patients with no apparent short-term adverse effects. The results support the use of low-dose short-term schedule ketorolac for pain control among orthopaedic polytrauma patients.

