Interventional Model Description: Compare the effectiveness of a NSAID to placebo in acute trauma setting.

Masking: Triple (Participant, Care Provider, Investigator)

Masking Description: Participant medical team will be blinded to the treatment or placebo intervention.

3. Outcome Measures

Primary Outcome: Length of Hospital Stay

Secondary Outcomes:

- Daily Concentrations of IL-1, IL-6, IL-10, and PGE2
- Incidence of Post-Traumatic Complications (e.g., bacterial pneumonia, SIRS, MODS, ARDS, and AKI)
- Mortality
- Visual Analogue Pain Scores
- Inpatient Morphine Milligram Equivalents
- Change in Inpatient Subjective Pain Reports
- Change in Outpatient Subjective Pain Reports

4. Background

Accidental trauma is the 4th leading cause of death in the United States, and it is associated with a complex inflammatory response. This response is associated with post-traumatic complications such as multi-organ dysfunction syndrome (MODS), bacterial pneumonia, acute respiratory distress syndrome (ARDS), systemic inflammatory response syndrome (SIRS), and post traumatic pain (PTP). It is unknown whether early modulation of inflammatory cytokines is associated with improved patient outcomes, reduced narcotic requirements, and improved patient subjective pain after hospital discharge.

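### Section 7 applies P<0.05 to every test and never labels the secondary outcomes as supportive, so a claim resting on any one secondary has no 5% error control

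*Combined protocol and SAP*

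**What the plan says.** Section 3 (Outcome Measures) gives "Primary Outcome: Length of Hospital Stay", and section 6 sizes the trial on LOS alone. The secondary list in section 3 has seven entries:

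- "Daily Concentrations of IL-1, IL-6, IL-10, and PGE2"
- incidence of post-traumatic complications, with five examples named
- mortality
- "Visual Analogue Pain Scores"
- "Inpatient Morphine Milligram Equivalents"
- change in inpatient subjective pain reports
- change in outpatient subjective pain reports

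Section 7 (Statistical Analysis Plan) compares log-transformed LOS by analysis of variance and assigns linear mixed models to VAS, MME and the cytokines. For the cytokines: "Time and group comparisons for each cytokine will be made using linear mixed models, with and without adjusting for selected covariates". The significance rule for all of this is one sentence: "Throughout the study, a P value of less than 0.05 will be considered significant".

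Neither the protocol nor the IRB application makes secondary testing conditional on LOS, divides alpha, ranks the secondaries or calls them supportive or exploratory.

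Item 7 of the continuation review, under the question on benefits, summarises results in 70 participants. It calls opioid intake (p = 0.0039) and VAS pain (p = 0.0481) significantly reduced on ketorolac and concludes: "The results support the use of low-dose short-term schedule ketorolac for pain control among orthopaedic polytrauma patients". No LOS result appears there.

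**The concern.** A P value below 0.05 carries a 5% false-positive risk for one test chosen in advance. Section 7 gives the same standing to the planned LOS comparison and to every secondary. A reader of the final report could therefore meet a secondary described as significant, with nothing in the plan to say that it counts for less than LOS or was one of about ten. If LOS showed no effect and one secondary fell below 0.05, the plan would not stop that secondary from carrying the conclusion. The continuation-review summary shows that this is a practical risk: its conclusion in favour of treatment rests on two secondaries.

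**Working it through.** **The plan's own figure.** Section 6 uses alpha 0.05, SD 1.5 days, a difference of 0.928 days and 80% power.

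- n per group = 2 × (1.960 + 0.842)² × 1.5² / 0.928² = 41.0, rounded up to 42.
- Exact t-test power at 42 per group is 80.0%.
- Dropout: 84 / (1 − 0.25) = 112.

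All stated figures reproduce with two-sided alpha 0.05. The whole 5% is spent once, on LOS, so the primary test is sound on this point.

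**Counting the secondaries (section 3).**

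- Four cytokines + complications as one outcome + mortality + VAS + MME + two pain-change outcomes = 10.
- If the inpatient pain change is the same measure as VAS: 9. Section 10e measures inpatient pain by VAS, and the schedule in section 9 lists no other pain measure.
- Outcomes to which section 7 assigns a mixed model (VAS, MME, four cytokines): 6.

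**Chance of at least one false positive.** Assume one two-sided test per outcome at 0.05, no true effect on any of them, and normal test statistics with a common correlation ρ. With c = 1.960:

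- ρ = 0: 1 − 0.95^k.
- ρ > 0: 1 − ∫ φ(x) [Φ((c − √ρ·x)/√(1−ρ)) − Φ((−c − √ρ·x)/√(1−ρ))]^k dx.

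| Outcomes (k) | ρ = 0 | ρ = 0.5 | ρ = 0.8 |
|---|---|---|---|
| 6 | 26.5% | 20.7% | 13.9% |
| 9 | 37% | 27% | 17% |
| 10 | 40.1% | 28.7% | 17.3% |

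The documents give no correlations, so the range across each row is the result and no single column is preferred.

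**What lowers these figures.**

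- *Assay rule.* Section 10e restricts analysis to analytes with a coefficient of variation below 20% if variation is wide. Losing one cytokine from the six gives 1 − 0.95⁵ = 22.6% at ρ = 0 and 12.7% at ρ = 0.8.
- *Rare binary outcomes.* Section 7 names Fisher exact tests for categorical measures. Assuming they are used for mortality and complications with 56 per group, the true size of each test is 0.06%, 0.9%, 2.0% and 2.8% at assumed event rates of 2%, 5%, 10% and 20%. With eight tests at 5% and two at these sizes, all independent, the ten-outcome figure falls from 40% to between 1 − 0.95⁸ × 0.9994² = 34% and 1 − 0.95⁸ × 0.972² = 37%.

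**What raises them.** Fitting each cytokine model with and without covariates adds treatment tests that are not counted here. The time contrasts do not add to false treatment claims.

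**The case against.** The best defence is that the plan already has the hierarchy that matters: one named primary, a sample size tied to it, and everything else headed as secondary. Many investigator-initiated trials stop there, and whether correctly labelled secondaries need formal control is partly convention. This stands to the extent that the LOS error rate is untouched and no formal adjustment is required. It does not settle the point, because section 7 gives secondaries the same word, significant, on the same criterion, and says nowhere that they are read differently.

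Four stronger readings are tempting and are not supported:

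- *That the plan authorises a recommendation on any one secondary.* Section 7 contains no success or recommendation rule. The gap is that it does not prevent such a claim.
- *That the calculated rates are floors, or rise much further if the five named complications are tested separately.* That list is open-ended, rare events tested by Fisher's method spend well under 5% each, and the assay rule and possible VAS overlap reduce the count.
- *That the reported VAS and MME findings fail once multiplicity is handled.* This depends on the family chosen. Pain and opioid use are the second stated aim of the IRB application. Holm across those two alone would pass both (0.0039 < 0.025; 0.0481 < 0.05), whereas Bonferroni over ten (0.05/10 = 0.005) would pass MME only.
- *That the summary shows section 7 in operation.* It covers 70 participants, answers a form question about benefits, is limited to pain control, and does not say which tests gave its P values. The IRB application plans t-tests and section 7 plans mixed models. The missing LOS result proves little on its own.

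**Conclusion.** The point holds as a gap in the plan's reporting rule. The primary comparison is unaffected. For the secondaries, the 0.05 threshold does not give 5% protection to a claim selected because its P value fell below it: the chance of at least one false positive is about 14–27% across the six outcomes with a named mixed model and 17–40% across ten. These ranges rest on equicorrelated normal tests, correlation from 0.8 to 0, and no true effect on any secondary; they are somewhat lower where Fisher tests of rare events or the assay rule apply. Even the narrower count is well above 5%, so the conclusion does not turn on the correlation or on the exact number of outcomes. The continuation-review summary illustrates the risk and does not measure it. The correction should be made, but it does not threaten the trial's main result.

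**What to change.** Replace the significance sentence in section 7 with:

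> Two-sided P<0.05 is the significance criterion for the primary comparison of LOS only. The secondary outcomes in section 3 are supportive. They are reported as estimates with 95% confidence intervals and nominal P values, and no claim of efficacy rests on them alone.

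Word the conclusions of the final report to match.

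A formal adjustment among the secondaries is not proposed. Its result would depend on the family chosen, and that choice would now be made after MME and VAS results by arm have been seen. The submitted summary need not be changed.

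The cost is one sentence and care in reporting, with no new data or patients. The real price is that VAS and MME can no longer be called significant on a nominal P<0.05, although their estimates and intervals would still be reported in full.
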